Aim: This prospective randomized multicenter study will compare the long-term safety and efficacy of Culotte stenting versus DK-Crush stenting in the treatment of the de-novo non-left main coronary bifurcation lesions with new generation everolimus-eluting stents.

Methods: Four-hundred patients, in whom a double-stenting technique is intended for the treatment of a non-left main de-novo coronary bifurcation lesion will be randomly assigned to Culotte stenting or to DK-crush stenting with an approved contemporary everolimus-eluting stent. As a part of usual care, patients will undergo 9-month angiographic follow-up with quantitative coronary angiography. Clinical follow-up is planned at 9-12 months. The primary study endpoint is the maximal percent diameter stenosis in the bifurcation lesion at 9 months. Secondary endpoints include binary restenosis (estimated by Quantitative Coronary Angiography (QCA) analysis), Target Lesion Revascularization (TLR), Freedom from Major Adverse Cardiac Events (MACE) and the rate of stent thrombosis according to the definition of the Academic Research Consortium (ARC definition). The study will have 80% power to detect a 25% decrease in the primary endpoint at p < 0.05 by Culotte stenting as compared with DK-Crush.

1. STUDY BACKGROUND

Provisional side branch stenting is the most frequently used type of treatment in coronary bifurcation lesions. When stenting of both the side branch and the main branch (double stenting) is needed - because of complex anatomy, dissection occurring during lesion preparation, TIMI flow < 2 or high residual stenosis > 75% - there is a variety of established technical approaches. The most common double stenting techniques in daily routine are TAP stenting, Culotte stenting and "double kissing "-Crush stenting.

Our recently published BBK 2 - study ¹ demonstrated a benefit of the Culotte technique as compared to TAP technique during PCI of de-novo coronary bifurcation lesions, with a significant reduction in in-stent restenosis (primary study endpoint). Moreover, the BBK 2 - study showed a trend to better clinical outcomes after Culotte stenting during the first year of the clinical follow-up (secondary study endpoints). The difference was mainly driven by significant reduction for in-stent restenosis of the side branch stent.

In China, [name] and his colleagues ² modified the initially introduced classic crush technique to the "double kissing"-crush technique. The DK-Crush technique is technically more challenging due to more procedural steps. The use of the DK-crush technique was assessed in several randomized trials: comparison with classic crush technique ³, with provisional T-stenting ⁴ and with Culotte ² (only for patients treated for distal left main stenosis). The DK-Crush technique was associated with a lower angiographic restenosis rate and as well as with lower reintervention rates during long-term clinical follow-up.

In Europe, the randomized multicenter Nordic II study ⁷ addressed the question whether classic Crush-stenting or Culotte-stenting achieves better angiographic and clinical outcome after PCI in bifurcation lesions. The results demonstrated no significant difference in respect to the primary study endpoint. Major adverse cardiac events (MACE) as primary study endpoint occurred in 3.7 % in the Culotte study arm as compared to 4.3 % in the Crush study arm (p = 0.87).

All previous studies on the DK-Crush technique were performed using first generation drugeluting stents (DES), which are no longer in use. Currently, no randomized study compared DK-crush with Culotte techniques in patients with non-left main bifurcation lesions using contemporary DES. However, recent data showed that the use of new-generation DES is associated with better clinical outcomes as compared to first-generation DES ^{5, 6}.

[figure not shown]
2. STUDY DESIGN

This study is a prospective, randomized, multicenter evaluation of the treatment of de-novo coronary bifurcation lesions comparing DK-crush stenting with Culotte stenting using approved modern third-generation DES.

The primary endpoint of this study is the maximal percent diameter stenosis within the bifurcation at 9 months, assessed by quantitative coronary angiography. In addition, the study will assess various safety parameters.

Four-hundred patients will be enrolled and randomly assigned to DK-crush stenting or to Culotte stenting of non-left main bifurcation lesions. Only CE-certified everolimus-eluting Synergy[™] and Synergy Megatron[™] stents must be used.

This study is an investigator-initiated trial, designed and conducted by the University Heart Center Freiburg · Bad Krozingen. Partial financial support is obtained by a scientific grant from Boston Scientific (BSI). Data from patients enrolled at participating study sites will be transferred after pseudonymization to a central database at the University Heart Center Freiburg • Bad Krozingen to perform final data analysis and to publish the results of the study.

Primary study endpoint:	Maximal % diameter stenosis in the bifurcation lesion (QCA)
Secondary study endpoints:	Binary restenosis; TLR; MACE/ Death/ MI / Stent-Thrombosis
Clinical Follow-up:	9 - 12 months

Assessment Schedule

Assessment	Screening	PCI	Pre- discharge	9 months ± 30 days	lf no Re – Angiography: 12 months ± 30 days
Inclusion/Exclusion criteria	х				
Informed consent signed	Х				
Medical History	х				
Angina pectoris and NYHA status	х			x	х
Creatine kinase (CK) and hs-troponin	х		х		
12 lead ECG	Х		х		
Medication History	Х	х		х	х
Adverse Event Monitoring		х	Х	х	х
Index Procedure		х			
Re – Angiography				х	

3. HYPOTHESIS

The hypothesis of this study is as follows:

In non left-main coronary bifurcation lesions (main vessel > 2.5mm, side branch > 2.25mm) including significant ostial side branch disease, Culotte stenting compared with DK-crush stenting reduces maximal percent diameter stenosis at the bifurcation at 9-month follow-up by 25 %.

4. STUDY ENDPOINTS

4.1 Primary study endpoint

The primary study endpoint is:

- Maximal percent diameter stenosis at the bifurcation at 9 months.

4.2 Secondary endpoints

The following secondary endpoints will be evaluated in this study:

- Binary restenosis (≥ 50% diameter stenosis) rate at any segment of the bifurcation at
 9 months post procedure
- Binary restenosis (≥ 50% diameter stenosis) in the main and side branch at 9 months post procedure.
- TLR of the main and side branch at 9-12 months post procedure. Intervening targetlesion revascularization is defined as any repeated percutaneous revascularization of the stented segment, including the 5-mm proximal and distal margins.
- MACE defined as death, myocardial infarction (according to the fourth universal definition of myocardial infarction, 2018), emergent cardiac bypass surgery, or TLR at 9-12 months.
- Device success defined as attainment of < 30% residual stenosis of the target lesion using drug-eluting stent (DES) in the main and side branch
- Procedure time, radiation time and volume of used contrast medium
- Post-procedure thrombotic stent occlusion at 9-12 months according to the Academic Research Consortium-criteria: Stent thrombosis is classified by the ARC definition as definite, probable, or possible and as early (0 to 30 days), late (31 to 360 days), or very late (>360 days). The definition of definite stent thrombosis requires the presence of an acute coronary syndrome with angiographic or autopsy evidence of thrombus or occlusion. Probable stent thrombosis includes unexplained deaths within 30 days after the procedure or acute myocardial infarction involving the target-vessel territory without angiographic confirmation. Possible stent thrombosis includes all unexplained deaths occurring at least 30 days after the procedure.
- Disabling stroke defined as stroke requiring inpatient rehabilitation or skilled nursing care.
- Bleeding classified as type 3-5 according to the BARC classification as follows:

Type 0: No bleeding

Type 1: Bleeding that is not actionable and does not cause the patient to seek unscheduled performance of studies, hospitalization, or treatment by a health-care professional; may include episodes leading to self-discontinuation of medical therapy by the patient without consulting a health-care professional.

Type 2: Any overt, actionable sign of hemorrhage (e.g., more bleeding than would be expected for a clinical circumstance, including bleeding found by imaging alone) that does not fit the criteria for type 3, 4, or 5 but does meet at least one of the following criteria: requiring nonsurgical, medical intervention by a health-care professional, leading to hospitalization or increased level of care, or prompting evaluation

Type 3:

Type 3a: Overt bleeding plus hemoglobin drop of 3 to < 5 g/dL* (provided hemoglobin drop is related to bleed), any transfusion with overt bleeding

Type 3b: Overt bleeding plus hemoglobin drop $\geq 5 \text{ g/dL}^*$ (provided hemoglobin drop is related to bleed), Cardiac tamponade, Bleeding requiring surgical intervention for control (excluding dental/nasal/skin/hemorrhoid), Bleeding requiring intravenous vasoactive agents

Type 3c: Intracranial hemorrhage (does not include microbleeds or hemorrhagic transformation, does include intraspinal), subcategories confirmed by autopsy or imaging or lumbar puncture, intraocular bleed compromising vision

Type 4:

CABG-related bleeding, perioperative intracranial bleeding within 48 h, reoperation after closure of sternotomy for the purpose of controlling bleeding, transfusion of \geq 5 U whole blood or packed red blood cells within a 48-h period, chest tube output more than or equal to 2L within a 24-h period

Type 5: Fatal bleeding Type 5a: Probable fatal bleeding; no autopsy or imaging confirmation but clinically suspicious Type 5b:

Definite fatal bleeding; overt bleeding or autopsy or imaging confirmation

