6.2 Laboratory Assessments

- 12-lead ECG prior to procedure and between 12 hours and 24 hours post-procedure or before hospital discharge
- CK and CKMB and Troponin T prior to procedure and at least once prior to discharge. If several pre- and post-procedure assessments are available, highest levels are reported.

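### The printed summary of probable stent thrombosis in section 4.2 can take in procedure-related infarctions, and it puts an unexplained death on day 30 in two classes

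*Protocol*

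**What the plan says.** The stent thrombosis bullet in Protocol section 4.2 opens with the endpoint and its standard: "Post-procedure thrombotic stent occlusion at 9-12 months according to the Academic Research Consortium-criteria". It then summarises the classes.

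- Timing: "as early (0 to 30 days), late (31 to 360 days), or very late (>360 days").
- Definite: "requires the presence of an acute coronary syndrome with angiographic or autopsy evidence of thrombus or occlusion".
- Probable: "Probable stent thrombosis includes unexplained deaths within 30 days after the procedure or acute myocardial infarction involving the target-vessel territory without angiographic confirmation".
- Possible: "Possible stent thrombosis includes all unexplained deaths occurring at least 30 days after the procedure".

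Under MACE, the same section defines "myocardial infarction (according to the fourth universal definition of myocardial infarction, 2018"). The stent thrombosis bullet itself names no definition of infarction. Section 6.2 calls for "CK and CKMB and Troponin T prior to procedure and at least once prior to discharge", with the highest values reported, and for an ECG before and after the procedure.

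Section 8 lists infarction and stent thrombosis as serious adverse events of special interest and asks for each event's causal relation to the procedure to be graded. The SAP says that clinical endpoints are analysed by intention to treat. It gives no definition of stent thrombosis.

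**The concern.** The infarction part of the probable class, "acute myocardial infarction involving the target-vessel territory without angiographic confirmation", is wide. An infarction caused by the index PCI in a treated vessel, in a patient not taken back to the catheter laboratory, meets it word for word. Such a patient may have no thrombosed stent.

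Stent thrombosis is a named secondary endpoint and a special-interest safety event. Section 1 describes DK-Crush as the more demanding technique because it has more steps. If procedural infarction differs between techniques, a literal reading would report that difference twice: once as infarction and again as stent thrombosis.

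Neither document describes an event committee, and section 8 takes event information from the treating physician. Classification therefore leans heavily on the printed wording.

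Separately, the boundary between probable and possible for unexplained deaths is not clean at day 30.

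**Working it through.** **Plan's own figure.** Neither document gives a rate for stent thrombosis or procedural infarction, so there is no figure for this endpoint to reproduce. The only computed figure is the 172 per arm in section 9, for the primary endpoint. It reproduces: a difference of 20/0.75 − 20 = 6.67 points, SD 22, two-sided 0.05 and 80% power give 171.9 per arm with the t-based formula. Nothing below depends on it.

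**Step 1: what the infarction part requires.** There are two conditions: an acute infarction in the target-vessel territory, and no angiographic confirmation. No time limit is attached to it and no alternative cause has to be ruled out. The early class begins at day 0, so the day of the procedure is inside the window.

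**Step 2: whether a procedural infarction can get there.**
- Markers are taken before PCI and at least once before discharge (6.2), so procedural rises are looked for.
- The routine final angiogram is taken at completion of the procedure (6.4.3), before those later markers.
- Section 6.5.1 analyses unscheduled angiograms where they exist but does not require one after a marker-defined infarction.
- The causality grade in section 8 shows that the protocol foresees procedure-related infarction, but nothing links that grade to the stent thrombosis class.

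The route is therefore open on the wording alone.

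**Step 3: size, under assumed rates.** Let s be the true stent thrombosis rate and p the rate of target-territory procedural infarction without a confirming angiogram, with no patient in both groups and the summary applied literally. Among 400 patients:
- added events = 400 × p
- chance of at least one = 1 − (1 − p)^400
- share of the reported count = p / (s + p)

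| p (assumed) | Added events | Chance of ≥ 1 | Share, s = 0.5% | Share, s = 1% | Share, s = 2% |
|---|---|---|---|---|---|
| 0.5% | 2 | 86.5% | 50% | 33% | 20% |
| 1% | 4 | 98.2% | 67% | 50% | 33% |
| 2% | 8 | 99.97% | 80% | 67% | 50% |
| 5% | 20 | about 100% | 91% | 83% | 71% |

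The extremes are 0.005 / (0.02 + 0.005) = 20% and 0.05 / (0.005 + 0.05) = 91%. At s = 1% the reported rate would be 1.5%, 2%, 3% or 6%.

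**Step 4: the day-30 boundary.** For an unexplained death:

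| Day of death | Probable (within 30) | Possible (at least 30) | Timing class |
|---|---|---|---|
| 29 | yes | no | early |
| 30 | yes | yes | early |
| 31 | no | yes | late |

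Only day 30 falls in two classes. The timing classes in the same bullet have no such overlap.

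**The case against.** The strongest reply is that the bullet is governed by the ARC criteria and is headed as thrombotic stent occlusion. An assessor told to classify by ARC would go to that source, and a next-day marker rise with no suspicion of occlusion fits the heading poorly. This stands as a limit: misclassification follows only if the summary is applied by itself. It does not remove the problem. The protocol prints a rule that can be applied alone, and its reference list has no entry for the ARC source. Two sites could therefore class the same patient differently. What the ARC text says is not in the documents and is not relied on here.

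Three stronger readings are tempting, and the documents do not support them.

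- *The stent thrombosis rate would be mainly a procedural infarction rate.* Every rate above is assumed, and the share runs from 20% to 91%. The documents do not settle where in that range the trial would fall.
- *The protocol's infarction definition itself brings procedural infarction into the class.* The fourth universal definition is cited by name only, and only under MACE. Its content is not reproduced.
- *All infarction attributed to the index PCI should therefore be excluded.* An early infarction without angiography may be a true stent thrombosis, and a blanket exclusion would hide it.

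There are also partial safeguards. Causality is graded and events are checked against source documents (section 8), so procedure-related events can be identified. Definite events need angiographic or autopsy evidence and are not affected. None of this corrects the wording of the probable class.

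**Conclusion.** The point holds as a defect of wording. The printed summary, applied alone, can score a procedure-related infarction as probable stent thrombosis, and neither the rest of the protocol nor the SAP closes that route. The possible share of 20% to 91% rests entirely on the assumed rates, on literal application and on no overlap between the two kinds of event. It shows that the effect need not be trivial, but it is not an estimate for this trial.

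The day-30 contradiction needs no assumption, but it will touch few patients, if any.

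This is a minor correction to a secondary endpoint. A reader should not infer any effect on the primary endpoint or the sample size.

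**What to change.** In Protocol section 4.2:

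1. State that the full ARC criteria prevail over the printed summary, and add the source to the reference list.
2. Reword the infarction part to: *acute myocardial infarction in the territory of the implanted stents, without angiographic confirmation of stent thrombosis and with no other evident cause*. Use the causality grade already recorded under section 8 to inform that judgement. Do not exclude every PCI-related infarction automatically.
3. For possible stent thrombosis, change the boundary to *more than 30 days*. Day 30 is then probable and early, and day 31 is possible and late.
4. Report definite, and definite plus probable, stent thrombosis by arm. Definite events do not depend on the disputed wording.

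The cost is a few sentences in the protocol, with matching eCRF guidance and a line in the SAP. No new data are needed. The downside is a smaller count of events, and some true early stent thromboses without angiography may be put down to the procedure.

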5. PATIENT SELECTION

This trial will include 400 symptomatic patients with a de novo bifurcation lesion of a native coronary artery who meet eligibility criteria and provide written informed consent for participation in the study.

Eligible subjects will be informed about the scope and potential risks of the study verbally and in written form (ICF) the day before PCI. Informed consent will be obtained at the subsequent day before any study-related procedure and before start of the PCI.

5.1 Inclusion Criteria

Patients will be enrolled only, if all the following conditions are met:

- Clinical indication, evidenced by angina/angina-equivalent symptoms or documented ischemia (non-invasive imaging such as scintigraphy, stress-MRI or stress-echo; FFR or iwFR) or patients with acute coronary syndromes (NST-ACS).
- 2. Clinical indication to perform double stenting only with Synergy[™] stents for a clinically significant bifurcation stenosis as judged by the operator.
- 3. De-novo non-left main coronary bifurcation lesions 1,1,1 or 0,1,1 according to the Medina classification - of a native coronary artery with the following reference vessel diameters: main branch > 2,5 mm; side branch > 2,25 mm. The difference between vessel diameter of the main and side branch is ≤ 1 mm.
- 4. The target lesion has not been previously treated with any interventional procedure.
- 5. The target vessel (main branch and side branch) must appear feasible for stent implantation.
- 6. Patient has no other coronary intervention planned within 30 days of the procedure.
- 7. Patient has been informed of the nature of the study and agrees to its provisions and has written informed consent as approved by the Ethics Committee.

8. Patient is willing to comply with all required post-procedure follow-up.

5.2 Exclusion Criteria

Patients are not eligible for enrollment into the study if any of the following conditions apply:

- 1. Patient had an acute ST-elevation myocardial infarction or target vessel contains intraluminal thrombus.
- 2. Use of any other coronary stent than Synergy[™] and Synergy Megatron[™] except for bail-out situations.
- 3. Patient with a known hypersensitivity or contraindication to the needed antithrombotic therapy, stent type or contrast media that cannot be adequately pre-medicated.
- 4. Non successful treatment of other lesion during the same procedure.
- Patient with a severe bleeding diathesis, history of recent major bleeding or stroke (≤ 6 months), coagulopathy or severe liver disease.
- Patient has a co-morbidity (i.e. cancer) that may cause the patient to be noncompliant with the protocol, or is associated with limited life-expectancy (less than 1 year).
- 7. Patient is participating in any other clinical study with an investigational product.
- 8. Patient is known to be pregnant or lactating at time of inclusion.

5.3 Randomization

Patients who fulfill inclusion and have no exclusion criteria and provided written informed consent to the study will be randomized to DK-Crush stenting or to Culotte-stenting using computer-generated random sequences stratified by investigation sites. The random sequence and block sizes per site will be selected by the statistician and will be unknown to the investigators and medical staff caring for the patients. Randomization will be performed immediately before catheter treatment of the bifurcation lesion.

6. STUDY ASSESSMENTS

6.1 Patient Enrollment

All potential subjects must be consented prior to performing any study related procedures. The investigator or representative will explain the nature and scope of the study, potential risks and benefits of participation, and answer questions for the patient. If the patient agrees to participate, informed consent must be signed and dated; a copy must be provided to the patient

Baseline data to be collected will include demographics, angiographic and clinical parameters.

6.2 Laboratory Assessments

- 12-lead ECG prior to procedure and between 12 hours and 24 hours post-procedure or before hospital discharge
- CK and CKMB and Troponin T prior to procedure and at least once prior to discharge. If several pre- and post-procedure assessments are available, highest levels are reported.

6.3 Concomitant Medications

All subjects receive the medication regimen listed below. All medications administered should be recorded in the subject's medical record.

Prior to Procedure

Aspirin Clopidogrel Prasugrel At least 400 mg per os 600 mg loading dose or 60 mg loading dose or

	Ticagrelor180 mg loading dosefor all: if not on chronic treatment	
During Procedure	IV Heparin IC Glyceryl trinitrate	For angioplasty bolus 100 I.U./ kg/ KG 100 – 200 mcg prior to baseline and post intervention angiograms
Post-Procedure	Aspirin Clopidogrel Prasugrel Ticagrelor	At least 100 mg per day indefinitely 75 mg per day for at least 6 months or 10 mg or 5 mg/day for at least 6 months as per drug label 2 x 90 mg /day for at least 6 months as per drug label

Glycoprotein IIb/IIIa inhibitors can be used for bail out.

6.4 Coronary Angiography and Intervention

6.4.1 Angiography

Using standard procedures for angioplasty, an introducer sheath of at least 6 French will be introduced and the heparin bolus will be administered. After introduction of the guiding catheter and following intra-coronary injection of nitroglycerin, baseline angiography of the vessel will be performed in at least two best views that show the target lesion free of foreshortening or vessel overlap.

